## 10. DRUG INFORMATION

### 10.1. Nivolumab

Nivolumab was selected for dosage form development and is also referred to as BMS-936558-01 or BMS-936558. Nivolumab is a soluble protein consisting of 4 polypeptide chains, which include 2 identical heavy chains and 2 identical light chains.

Other Names Nivolumab, BMS-936558, MDX1106, anti-PD-1

Molecular Wt 146,221 daltons (143,619.17 daltons, protein portion)

Appearance Clear to opalescent, colorless to pale yellow liquid, few particulates may be present

Solution pH 5.5 to 6.5

#### 10.1.1. Supplier/How Supplied

Nivolumab Injection, 100 mg/10 mL (10 mg/mL) vials. There are five nivolumab 100-mg vials per carton.

BMS will supply nivolumab as investigational supply at no charge to subjects participating in this clinical trial.

The site investigator shall take responsibility for and shall take all steps to maintain appropriate records and ensure appropriate supply, storage, handling, distribution, and usage of investigational product in accordance with the protocol and any applicable laws and regulations.

#### **10.1.2. Preparation**

Visually inspect drug product solution for particulate matter and discoloration prior to administration. Nivolumab is a clear to opalescent, colorless to pale-yellow solution. Discard the vial if the solution is cloudy, discolored, or contains extraneous particulate matter other than a few translucent-to-white, proteinaceous particles. Do not shake the vial.

- Withdraw the required volume of nivolumab and transfer into an intravenous container.
- Dilute nivolumab with either 0.9% Sodium Chloride Injection, USP or 5% Dextrose Injection, USP to prepare an infusion with a final concentration ranging from 1 mg/mL to 10 mg/mL.
- Mix diluted solution by gentle inversion. Do not shake.
- Discard partially used vials or empty vials of nivolumab.
- The maximum allowable volume of final infusion is 120 mL.

#### **10.1.3. Storage and Stability**

The product does not contain a preservative.

After preparation, store the nivolumab infusion either:

- At room temperature for no more than 8 hours from the time of preparation. This includes room temperature storage of the infusion in the IV container and time for administration of the infusion or
- Under refrigeration at 2°C to 8°C (36°F to 46°F) for no more than 24 hours from the time of infusion preparation.

Do not freeze.

#### **10.1.4. Administration**

Administer the infusion over 30 minutes (acceptable window is 25 minutes to 40 minutes) through an intravenous line containing a sterile, non-pyrogenic, low protein binding in-line filter (pore size of 0.2 micrometer to 1.2 micrometer).

Do not coadminister other drugs through the same intravenous line. Flush the intravenous line at end of infusion.

#### **10.1.5. Handling and Disposal**

Preparation should be performed by trained personnel in accordance with good practices rules, especially with respect to asepsis.

#### **10.1.6. Accountability**

The investigator, or a responsible party designated by the investigator, should maintain a careful record of the inventory and disposition of the agent using the NCI Drug Accountability Record Form (DARF) or another comparable drug accountability form. (See the NCI Investigator's Handbook for Procedures for Drug Accountability and Storage.)

#### **10.1.7. Dispensing**

Nivolumab must be dispensed only from official study sites and to eligible subjects under the supervision of the site investigator. Nivolumab should be stored in a secure area according to local regulations. It is the responsibility of the site investigator to ensure that study drug is only dispensed to subjects.

#### **10.1.8. Adverse Events**

The most common side effects of nivolumab are:

- Fatigue
- Skin reactions: including rash, itching, hives, redness, and dry skin.
- Diarrhea
- Nausea
- Abdominal pain
- Decreased appetite
- Low red blood cells
- Fever
- Joint pain or stiffness

Less common side effects of nivolumab include:

- Bowel inflammation
- Liver function blood test abnormalities
- Loss of color (pigment) from areas of skin
- Dry mouth
- Vomiting
- Weight loss

- Thyroid gland abnormalities
- Blood chemistry abnormalities, including low blood phosphate, magnesium, and potassium levels.
- High blood uric acid level
- Lung inflammation (pneumonitis - see details below)
- Cough
- Dizziness
- Headache
- Low white blood cells
- Chills
- Muscle soreness, weakness, stiffness spasms or paralysis
- Pain in arms or legs
- Tingling, burning, or numbness in hands and feet
- Shortness of breath
- Abnormal taste
- Flushing
- High or low blood pressure
- Allergic reaction during or between study drug infusions
- Increased sensitivity of skin to sunlight
- Constipation
- Difficulty swallowing
- Heartburn
- Low blood platelets (may increase risk of bleeding)

Rare but potentially serious side effects of nivolumab include:

- Low blood oxygen level
- Acute lung injury or failure
- Collection of fluid around the lungs
- Inflammation of the appendix
- Increase in inflammatory blood proteins (e.g., lipase)
- Adrenal gland abnormalities
- Pituitary gland inflammation
- Changes in vision (including decreased or blurry vision), inflammation of the eye, or bleeding into the eye
- Liver inflammation
- Acute kidney injury or failure
- Abnormal blood cell production
- Inflammation of the mouth and lining of the digestive tract
- Swelling of the face, arms, or legs
- Inflammation of the pancreas
- Back pain
- Autoimmune disorders, including Guillain-Barre syndrome (associated with progressive muscle weakness or paralysis)
- Chest discomfort

- Heart palpitations
- Inflammation of the heart or its lining
- Collection of fluid around the heart
- Increased blood sugar
- Dehydration
- Infections: including sepsis, lung infections, and skin infections.
- Decreased movement of the intestines
- Disorientation
- Swelling of the optic disc
- Inflammation of the optic nerve
- Inflammation or loss of the lining of the brain and spinal cord
- Drug reaction with rash, blood cell abnormalities, enlarged lymph nodes, and internal organ involvement (including liver, kidney, and lung); known as Drug Reaction with Eosinophilia and Systemic Symptoms (DRESS)
- Myasthenia gravis, a nerve disease that may cause weakness of eye, face, breathing, and swallowing muscles.
- Abnormal brain function due to brain inflammation.
- Rhabdomyolysis (muscle fiber released into the blood stream which could damage your kidney) and polymyositis (chronic muscle inflammation with muscle weakness) has been reported in one subject.
- Lung inflammation or pneumonitis

## **11. ADVERSE EVENTS**

The descriptions and grading scales found in the NCI CTCAE version 5.0 will be utilized for AE assessment. A copy of the CTCAE v5 can be downloaded from the CTEP website at <http://ctep.cancer.gov>. All forms for AE/SAE recording and reporting can be found in OnCore (Documents and Information Tab).

### **11.1. Definitions**

#### **11.1.1. Adverse Event (AE)**

An AE is any untoward medical occurrence whether or not considered related to the study drug that appears to change in intensity during the course of the study. The following are examples of AEs:

- Unintended or unfavorable sign or symptom
- A disease temporally associated with participation in the protocol
- An intercurrent illness or injury that impairs the well-being of the subject

Abnormal laboratory values or diagnostic test results constitute AEs only if they induce clinical signs or symptoms or require treatment or further diagnostic tests

Hospitalization for elective surgery or routine clinical procedures that are not the result of an AE (e.g., surgical insertion of central line) should not be recorded as an AE.

Disease progression should not be recorded as an AE, unless it is attributable to the study regimen by the site investigator.

### 11.1.2. Serious Adverse Event (SAE)

A SAE is an adverse event that:

- Results in death. **NOTE:** Death due to disease progression should not be reported as a SAE, unless it is attributable by the site investigator to the study drug(s)
- Is life-threatening (defined as an event in which the subject was at risk of death at the time of the event; it does not refer to an event which hypothetically might have caused death if it were more severe)
- Requires inpatient hospitalization for >24 hours or prolongation of existing hospitalization. **NOTE:** Hospitalization for anticipated or protocol specified procedures such as administration of chemotherapy, central line insertion, metastasis interventional therapy, resection of primary tumor, or elective surgery, will not be considered serious adverse events.
- Results in persistent or significant disability/incapacity
- Is a congenital anomaly or birth defect
- Is an important medical event (defined as a medical event(s) that may not be immediately life-threatening or result in death or hospitalization but, based upon appropriate medical and scientific judgment, may jeopardize the subject or may require intervention (e.g., medical, surgical) to prevent one of the other serious outcomes listed in the definition above). Examples of such events include, but are not limited to, intensive treatment in an emergency room or at home for allergic bronchospasm; blood dyscrasias or convulsions not resulting in hospitalization; or the development of drug dependency or drug abuse.

### 11.1.3. Unexpected Adverse Event

For this study, an AE is considered unexpected when it varies in nature, intensity or frequency from information provided in the current IB, prescribing information or when it is not included in the informed consent document as a potential risk.

Unexpected also refers to AEs that are mentioned in the IB as occurring with a class of drugs or are anticipated from the pharmacological properties of the drug, but are not specifically mentioned as occurring with the particular drug under investigation.

### 11.1.4. Relatedness

AEs will be categorized according to the likelihood that they are related to the study drug(s). Specifically, they will be categorized using the following terms:

Unrelated	Adverse Event is not related to the study drug(s)
Unlikely	Adverse Event is doubtfully related to the study drug(s)

Possible	Adverse Event may be related to the study drug(s)
Probable	Adverse Event is likely related to the study drug(s)
Definite	Adverse Event is clearly related to the study drug(s)

### 11.1.5. Pregnancy

Any pregnancy that occurs in a female partner of a male study participant should be reported within 24 hours of knowledge of the event to BMS WorldWide Safety using either the MedWatch form. Information on this pregnancy will be collected on the Pregnancy Surveillance Form. In order for Sponsor or designee to collect any pregnancy surveillance information from the female partner, the female partner must sign an informed consent form for disclosure of this information. Details on the pregnancy will be collected for safety analysis throughout the pregnancy and for one year following the birth of the infant. After obtaining the subject's consent (or subject and pregnant partner's consent in the case of a male participant), monitoring of the pregnancy and infant should comply the following procedures:

- If the outcome is an abnormal neonate (infant), as much follow up information as possible to permit evaluation of the case will be collected, including where possible, medical confirmation, medical investigations and medical record summary details. Follow up should continue for one year post birth.
- If the outcome is a normal neonate, follow up data should continue for one month

### 11.1.6. Overdose

An overdose is defined as the accidental or intentional administration of any dose of a product that is considered both excessive and medically important. All occurrences of overdose must be reported as a SAE.

## 11.2. Reporting

Each participating investigator is required to abide by the reporting requirements set by the DF/HCC. The study must be conducted in compliance with FDA regulations, local safety reporting requirements, and reporting requirements of the principal investigator.

Each investigative site will be responsible to report SAEs that occur at that institution to the DFCI Office for Human Research Studies (OHRS) per the DFCI IRB reporting policy.

### 11.2.1. Adverse Events

- AEs will be recorded from time of signed informed consent until 100 days after discontinuation of study drug(s).
- AEs will be recorded regardless of whether or not they are considered related to the study drug(s).
- All AEs will be recorded in the subject's medical record and on the appropriate study specific eCRF form within OnCore.
- AEs considered related to study drug(s) will be followed until resolution to Grade  $\leq 1$  or baseline, deemed clinically insignificant, and/or until a new anti-cancer treatment starts, whichever occurs first.

### 11.2.2. Serious Adverse Events (SAEs)

#### 11.2.2.1. Site Requirements for Reporting SAEs

All serious adverse events that occur after the subject's written consent to participate in the study, during treatment, or within 100 days of the last dose of treatment must be reported to the DF/HCC Overall Principal Investigator and BMS WorldWide Safety on the local institutional SAE form, whether or not related to nivolumab treatment and including those thought to be associated with protocol-specified procedures.

Note: If the participant is in long term follow up, report the death at the time of continuing review.

Participating investigators must report each serious adverse event to the DF/HCC Overall Principal Investigator as well as the Bristol-Myers Squibb Safety Department within 24 hours of learning of the occurrence. In the event that the participating investigator does not become aware of the serious adverse event immediately (e.g., participant sought treatment elsewhere), the participating investigator is to report the event within 24 hours after learning of it and document the time of his or her first awareness of the adverse event. The local institutional SAE form or Medwatch SAE form (<https://www.accessdata.fda.gov/scripts/medwatch/index.cfm?action=reporting.home>) should be completed for any event where doubt exists regarding its status of seriousness. Note: Please include the BMS Protocol number on the SAE form or on the cover sheet with the SAE form transmission

Report serious adverse events by email or facsimile to both:

DF/HCC Overall Principal Investigator and Medical Monitor:  
[name]  
[contact]  
[[contact]](mailto:[contact])  
[contact]

**AND**

Bristol-Myers Squibb:  
SAE Email Address: [contact]  
SAE [contact]

Within the following 24-48 hours, the participating investigator must provide follow-up information on the serious adverse event. Follow-up information should describe whether the event has resolved or continues, if and how the event was treated, and whether the participant will continue or discontinue study participation.

Participating investigators will report to their local Risk Management office any participant safety reports, sentinel events or unanticipated problems that require reporting per institutional policy.

**11.2.3. Monitoring of Adverse Events and Period of Observation**

All adverse events, both serious and non-serious, and deaths that are encountered from initiation of study intervention, throughout the study, and within 100 days of the last study intervention should be followed to their resolution, or until the participating investigator assesses them as stable, or the participating investigator determines the event to be irreversible, or the participant is lost to follow-up. The presence and resolution of AEs and SAEs (with dates) should be documented on the appropriate case report form and recorded in the participant's medical record to facilitate source data verification.

For some SAEs, the Principal Investigator or designee may follow-up by telephone, fax, and/or monitoring visit to obtain additional case details deemed necessary to appropriately evaluate the SAE report (e.g., hospital discharge summary, consultant report, or autopsy report).

Participants should be instructed to report any serious post-study event(s) that might reasonably be related to participation in this study. Participating investigators should notify the DF/HCC Overall Principal Investigator of greater or equal to grade 3 events and the IRB of any unanticipated death or adverse event occurring after a participant has discontinued or terminated study participation that may reasonably be related to the study.

At the end of the study period, Bristol-Myers Squibb Company will not continue to supply study drug to subjects/investigators. The investigator is responsible to ensure that the subject receives appropriate standard of care or other appropriate treatment in the independent medical judgement of the Investigator to treat the condition under study.

#### **11.2.4. Reporting to the Food and Drug Administration (FDA)**

The Overall PI, as study sponsor, will be responsible for all communications with the FDA. The Overall PI will report to the FDA, regardless of the site of occurrence, any serious adverse event that meets the FDA's criteria for expedited reporting following the reporting requirements and timelines set by the FDA.

## **12. STATISTICAL METHODS**

### **12.1. Power Calculation and Sample Size Justification**

We plan to enroll 34 patients into the study (with 20 in the PD-L1-positive cohort and 14 in the PD-L1-negative cohort). We hypothesize that patients with positive PD-L1 status will respond better to therapy, but we do not have enough power for formal comparisons between patients with and without positive PD-L1 status.

In 20 patients with PD-L1-positive status, if 2 or more patients achieved disease control at 12 weeks, we would consider the study a success. With 20 patients, there is 97% power to detect a 25% disease control rate (from null of 1%) with one-sided alpha of 0.02 using a one-sample binomial test. A null hypothesis of 1% was chosen since we do not expect any patients to achieve disease control without receiving any intervention.

With 14 patients having PD-L1-negative status, the probability of seeing 0 response is 4.4% if the true rate of disease control is 0.2. There is 96% power to detect a 20% disease control rate vs. null of 1% DCR at one-sided alpha=0.13 (target alpha 0.15, target power 0.95). We would like to be able to see at least 1 patient achieving disease control at 12 weeks in order to consider the regimen promising for future testing in the PD-L1-negative population. The 96% power (a small false negative rate) while allowing larger alpha is to ensure we do not miss any potential drug activity in patients with PD-L1-negative status.

### **12.2. Assessment of Efficacy**

#### **12.2.1. Primary analysis**

Patients with disease control at 12 weeks will be summarized as number and proportion with 90% CI for the 20 patients with PD-L1 positive status and 14 patients with PD-L1 negative status separately.

Patients that are considered un-evaluable for the primary endpoint by never starting treatment will be replaced.

#### **12.2.2. Secondary analysis and analysis of safety**

Maximum PSA change and best PSA response will be summarized descriptively and graphically in waterfall plots. PSA doubling time will be calculated with linear regression model of natural logarithm of PSA and time. PSADT at baseline and

EOS will be summarized, and change in PSADT, as captured by the change in PSA slope, will be summarized descriptively as well. Time to event endpoints will be summarized using Kaplan Meier estimate.

All reported toxicities, regardless of attribution, will be summarized by toxicity type and maximum grade. The maximum grade consolidates the reports of a given toxicity for a patient over time by taking the maximum across time. Immune modulatory medication used for toxicities will also be summarized descriptively.

### **12.3. Exploratory Analyses**

The exploratory analyses will proceed with all 34 enrolled patients combined if responses are observed. The markers of interest are described in Section 8.1. Some objectives will explore the relation among markers, and some will explore markers (e.g., PD-L1 expression, CD8+ TILs, change in plasma cytokines or PBMC subsets from pre-treatment to post-1 cycle) in relation to with disease control on nivolumab. With the given sample size and low expected disease control rate, all results will be considered as preliminary. Analyses will include descriptive and graphical summaries, using scatterplots and estimating correlation coefficients among continuous markers (including the % change in PSA at 12 weeks as continuous value), and using boxplots of marker levels according to the disease control endpoint. Hypothesis testing may be undertaken if there are several patients who experience disease control (more than say 4 or 5) of the hypothesis that greater expression of PD-L1 and/or CD8+ TILs is associated with higher probability of disease control, using Wilcoxon rank sum tests if the marker has a continuous distribution, or Fisher's exact test if an established cutpoint of the distribution exists.

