## 1.9. Rationale for the Current Trial

Despite the successes of programmed death-1 (PD-1)/programmed-death ligand-1 (PD-L1) inhibitors in other solid tumors, no objective responses were observed in phase I trials in prostate cancers. Treatments were well tolerated, with grade 3-4 drug-related adverse events occurring in 18% of patients at most (many of these being laboratory, not clinical events). One concern was that PD-L1 might be insufficiently expressed, as suggested in early reports in primary and in metastatic castration-resistant prostate cancer (mCRPC). Prostate cancer also has been suggested to have a relatively low overall mutation rate compared to solid tumors that demonstrate response, such as bladder and lung cancer. However, subsequent studies—in primary PCa rather than mCRPC, with much larger sample sizes, and using newer antibodies—suggested PD-L1 expression rates of 20-60% or as high as 92%. Additionally, tumor PD-L1 expression significantly correlated with risk of BCR, suggesting the BCR population might be especially enriched for PD-L1 expression and that inhibition of innate immune function could be associated with more aggressive disease. Similarly, PD-L1 expression may be affected by hormonal manipulation; in particular, it may decrease after ADT with abiraterone, suggesting that hormone-naïve PCa could be enriched for PD-L1 expression. Finally, immune-suppressive immune cells such as myeloid-derived suppressor cells may be increased in the setting of castration resistance, suggesting that

the tumor microenvironment may be quite different in earlier stages of disease and therefore justifying a new trial in this space. The presence of immune-suppressive immune cells could also represent a potential mechanism of resistance to this strategy, as well as a target for future interventions.

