## **2.2. Endpoints**

### **2.2.1. Primary Endpoint**

The primary endpoint is disease control, defined as PSA at 12 weeks less than 10% above baseline, or below baseline, and no symptomatic/radiographic progression, after 12 weeks of nivolumab treatment.

The expected increase in PSA at 12 weeks depends on doubling time. Based on the doubling time formula,  $\text{doubling time} = \log(2)/\log(1 + \text{growth rate})$ , a patient with a 10-month doubling time (the longest allowed under the exclusion criteria) would be expected to have an approximately 7.18% growth rate per month. PSA increase over 3 months (12 weeks) without intervention would be expected to be 23%. Faster doubling time would result in faster growth rate. Therefore, disease stability will be considered a PSA rise of less than 10% above baseline at 12 weeks. (This is in contrast with PCWG3, which considers PSA progression to be rise of at least 25% of baseline; as noted above, this criterion is too lenient in this setting given the expected PSA rise in the absence of intervention).

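### Marker correlations in Section 12.3 use raw 12-week % PSA change without baseline PSADT, so a marker of growth rate can pass for a marker of resistance or of benefit

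*Combined protocol and SAP*

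**What the plan says.** Section 12.3 sets out the marker analyses: "The exploratory analyses will proceed with all 34 enrolled patients combined if responses are observed". For continuous markers it plans scatterplots and "estimating correlation coefficients among continuous markers (including the % change in PSA at 12 weeks as continuous value". For disease control it plans boxplots and, if more than about four or five men reach it, possible Wilcoxon or Fisher tests. No covariate is named in either case, and the trial has no control arm.

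Section 2.2.1 states that "The expected increase in PSA at 12 weeks depends on doubling time" and that "Faster doubling time would result in faster growth rate". Its worked example is a man with a "10-month doubling time (the longest allowed under the exclusion criteria"), who "would be expected to have an approximately 7.18% growth rate per month"; it adds that "PSA increase over 3 months (12 weeks) without intervention would be expected to be 23" per cent. Sections 3.1 and 9.1 require a baseline PSADT for every man, from at least three PSA values spanning 8 weeks to 12 months. Section 3.1 sets an upper limit on PSADT but no lower one.

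Section 12.2.2 summarises baseline PSADT, end-of-study PSADT and the change in PSA slope. These summaries are descriptive and are not linked to any marker.

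Section 1.9 reports that "tumor PD-L1 expression significantly correlated with risk of BCR" and raises the possibility that immune inhibition goes with more aggressive disease.

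**The concern.** The exploratory question is whether a marker goes with response to nivolumab. Without a control arm, the only reference for what a man's PSA would have done untreated is his own pre-study slope. Raw % change ignores that reference. It mixes the growth rate a man brought into the trial with whatever the drug did to it.

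If a marker is associated with growth rate, the two cannot be separated. A marker of fast growth would go with larger PSA rises and be read as resistance; a marker of slow growth would be read as benefit. For PD-L1, the plan's lead marker, Section 1.9 gives some reason to suspect an association with aggressive disease. The error to fear there is a real benefit hidden by faster underlying growth. Section 1.9 says the data are meant to support a larger trial that asks, among other things, whether PD-L1 is associated with disease control. A misleading marker signal could therefore carry forward.

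**Working it through.** **1. The plan's own figure.** From the doubling-time formula in Section 2.2.1, monthly growth at PSADT 10 months is 2^(1/10) − 1 = 7.18%, and the 3-month rise is 2^(3/10) − 1 = 23.1%. Both match the text. Taking 12 weeks as 84 days (84/30.4375 = 2.76 months) gives 2^(2.76/10) − 1 = 21.1%.

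**2. The same formula for other eligible men, no drug effect.** Rise = 2^(t/PSADT) − 1.

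| PSADT (months) | t = 2.76 months | t = 3 months |
|---|---|---|
| 10 | 21% | 23% |
| 8 | 27% | 30% |
| 6 | 38% | 41% |
| 4 | 61% | 68% |
| 3 | 89% | 100% |
| 2 | 160% | 183% |

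Between PSADT 10 and 2 months the expected rise differs about eight-fold (183/23 = 8.0; 160/21 = 7.6).

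**3. The binary endpoint.** To stay below a 10% rise at 12 weeks, a man needs an on-treatment PSADT above 2.76/log2(1.1) = 20.1 months. That is a 2.0-fold lengthening from 10 months but 20.1/3 = 6.7-fold from 3 months. The disease-control comparisons therefore share the problem in a weaker form.

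**4. Size under a null drug.** The documents give neither the PSADT distribution nor the PSA noise, so these are assumptions: 34 men, PSADT uniform over the range shown, residual SD on the 12-week change in ln(PSA) as shown, no drug effect. The share of variance in log PSA change explained by growth rate is:

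| PSADT range (months) | Residual SD | Share explained |
|---|---|---|
| 2–10 | 0.12 | about 70% |
| 2–10 | 0.20 | about 46% |
| 4–10 | 0.12 | about 31% |
| 6–10 | 0.12 | about 11% |

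Take a marker correlated 0.3 with growth and unrelated to drug effect. A nominal 5% Spearman test against the 12-week change rejects in about 7% of trials for PSADT 6–10 months, and in about 23–24% for 2–10 months with SD 0.12. Virtually all these rejections are in the direction of resistance. A separate model, with explicit PSA measurement error (CV 5–15%) and within-man drift in growth rate, gives a similar picture: 15–33% for PSADT spread over 2–10 or 3–10 months, about 6% for 6–10 months, and about 5% for a marker unrelated to growth.

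**5. What adjustment achieves.** With the marker correlated 0.3, PSADT 2–10 months and SD 0.12, a rank-partial correlation given baseline slope brings rejection to about 7–9% if the slope carries 25% error, and to about 15–16% if it carries 50%. In the second model, with three pre-study PSAs over 6 months and a separate cycle 1 day 1 value, change in ln(PSA) slope rejects in 4–6% of trials.

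**6. How noisy the baseline slope can be.** For three equally spaced PSAs, SE(slope) = CV × √2/span. Over 8 weeks (1.84 months), with an assumed CV of 5–10%, this is 0.038–0.077 per month. The slope itself is ln2/6 = 0.116 at PSADT 6 months and ln2/10 = 0.069 at 10 months. The relative error is then 33–66% and 55–111% respectively, and smaller over longer spans.

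**The case against.** Several counter-arguments have force.

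- **Direction.** A reader might infer that a marker of aggressive disease would be mistaken for a marker of nivolumab effect. It would not: such a marker goes with larger rises. The only named test hypothesis in Section 12.3 is that greater PD-L1 or CD8+ TIL expression goes with more disease control. If PD-L1 tracks growth, the bias works against that hypothesis. This stands, and the risk for PD-L1 is masking.
- **Size.** A reader might infer that 12-week change mostly reflects natural doubling time. That is true in the plan's noise-free formula but is not established for the enrolled men. With SD 0.20 the share falls below half, and with PSADT 6–10 months it is about a tenth. This stands.
- **The PD-L1 premise.** Section 1.9 reports a correlation with the risk of recurrence, and every enrolled man has already recurred. The documents report no correlation between PD-L1 and PSADT, so 0.3 is an assumption. This stands.
- **The test.** Section 12.3 estimates this correlation; any formal test uses disease control. The analyses also go ahead only if responses are seen, a condition the simulations do not impose. The rejection rates are therefore illustrative, but the bias in the estimate is the same.
- **Already handled.** Section 12.2.2 reports change in PSA slope. It is not linked to markers, uses the last three PSAs before the end of treatment rather than the first 12 weeks, and cannot be computed for men who stop before cycle 4. This does not answer the point.
- **Exploratory status.** Results are labelled preliminary and hypothesis-generating. That limits the consequence, but a warning about imprecision does not correct a foreseeable bias.

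**Conclusion.** The concern holds in limited form. Section 12.3 relates markers to an outcome that Section 2.2.1 says depends on doubling time, and makes no use of the baseline PSADT that every man must have. A growth-related marker can then correlate with PSA change under an inert drug, appearing as resistance if it marks fast growth and as benefit if it marks slow growth.

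The size ranges from slight to material. Growth explains roughly 10% (PSADT 6–10 months) to 70% (2–10 months, residual SD 0.12) of the variance in log PSA change. A marker correlated 0.3 with growth reaches nominal p<0.05 in about 7% to 23% of null trials. These figures rest on the assumed PSADT spread, noise and marker correlation.

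Nothing here touches the primary endpoint or the success rules of 2 of 20 and 1 of 14, and the marker results remain hypothesis-generating either way.

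**What to change.** In Section 12.3, replace raw % change as the main continuous response with one of two measures:

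- the change in ln(PSA) from baseline to week 12, related to each marker with adjustment for the man's baseline ln(PSA) slope (partial Spearman, or slope as a regression covariate); or
- the change in ln(PSA) slope from the pre-study period to the first 12 weeks.

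Name the choice in advance. Show raw % change alongside as a descriptive plot, and list baseline PSADT beside each disease-control case. Do not split the disease-control tables by PSADT: with so few cases expected, most cells would be nearly empty.

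The cost is a few lines of text, since the data are already collected for eligibility. The drawback is that a slope from as few as three PSAs over 8 weeks is noisy, so adjustment reduces the confounding without removing it. The section should say so.
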